2.2 Endpoints

Primary performance endpoints

- Sensitivity: Proportion of spontaneous hypoglycaemic episodes detected by the hyposafe H02 compared to the total number of validated¹ spontaneous hypoglycaemic episodes after 12 weeks of monitoring (from visit 5 to visit 10)
- Positive predictive value: Proportion of validated¹ spontaneous hypoglycaemic episodes detected by the hyposafe H02 compared to the total number of alerts from the hyposafe H02 after 12 weeks of monitoring (from visit 5 to visit 10)

Secondary performance endpoints

- Overall sensitivity: Overall proportion of hypoglycaemic episodes detected by the hyposafe H02 compared to the total number of validated² hypoglycaemic episodes after 12 weeks of monitoring (from visit 5 to visit 10)
- Overall positive predictive value: Overall proportion of validated² hypoglycaemic episodes detected by the hyposafe H02 compared to the total number of alerts from the hyposafe H02 after 12 weeks of monitoring (from visit 5 to visit 10)
- Sensitivity: Proportion of insulin-induced hypoglycaemic episodes detected by the hyposafe H02 compared to the total number of insulin-induced hypoglycaemic episodes

¹ Validated by self-measured blood glucose (SMBG) or clinical hypoglycaemia according to subject's experience

² Validated by self-measured blood glucose (SMBG), plasma glucose (PG) or clinical hypoglycaemia according to subject's experience

- Positive predictive value: Proportion of insulin-induced hypoglycaemic episodes detected by the hyposafe H02 compared to the total number of alerts from the hyposafe H02
- Number of participants with a satisfactory EEG Quality test
- Change in impedance (from visit 5 to visit 10)
- Number of device complaints (from visit 4 to visit 10)
- Mean glucose level at the time of a hypoglycaemia alarm

Primary safety endpoint

- Number of AEs 17 weeks after implantation (from visit 3 to visit 12)

Secondary safety endpoint

- Number of adverse device effects (ADEs) 17 weeks after implantation (from visit 3 to visit 12)

Secondary usability endpoints

- Development in discomfort over time (visit 5 to visit 10)
- User satisfaction (visit 8)
- Mean number of hours of use per hyposafe H02 device (from visit 4 to visit 10)
- Response to hypoglycaemia alarm (from visit 5 to visit 10)
- Assessment of alarm fatigue (visit 12)

3 Study design - overview

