4.4 Withdrawal criteria

1. The subject may withdraw at will at any time without explanation
2. The subjects may be withdrawn from the study at the discretion of the investigator due to a safety concern or if judged non-compliant with the study procedures

Subjects must be withdrawn from the study for any of the following reasons:

3. Included in the study in violation with any of the inclusion and/or exclusion criteria
4. Use of any drug listed under exclusion criteria
5. Subject becomes pregnant during the study

This will not impact the treatment or follow-up of the subject. If a subject is withdrawn from the study, the investigator must aim to undertake procedures similar to those for visit 11 and 12: The

⁵ in Danish: 21 “genstande” per week

⁶ Safe anticonceptive methods includes contraceptive pills, intrauterine device including hormone intrauterine device and sustained gestagen injection

device must be explanted as quickly as possible, the sutures removed when appropriate and the end-of-study-form in the case report form (CRF) must be filled out.

Although a subject is not obliged to give his/her reason(s) for withdrawal, the investigator must make a reasonable effort to ascertain the reason(s), while fully respecting the subject's rights. Any reasons obtained must be specified in the subject's medical file and the appropriate section of the CRF.

5 Description of the hyposafe H02 device

The hyposafe H02 device consists of three parts: An implantable part which consists of a 20 mm semi-spherical implant house and an electrode (diameter: 1 mm, length 100 mm), see Figure 1b. The implant records the EEG signal and transmits the signal wirelessly to the external device. The position of the implant is depicted in Figure 1a. The external device is supplied in two versions: An ear hanger (Figure 1c) and a disc version (Figure 1d) both wirelessly receiving signals from the implant and charging the implant. An insertion needle for the implantation procedure (Figure 1e).

[figure not shown]

Figure 1 Hyposafe H02 device

a) Position of the implant and the external part of the device, b) The implant (left) consists of an electrode and an implant house. The external part (right) demonstrates the earhanger alone, c) Earhanger version of the external device, d) Disc version of the external device, e) Needle for insertion of the electrode

6 Methods and assessments

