6.1 Visit procedures

Procedure for scheduled visits and telephone contacts are described in the following and in the flow chart (Table 1).

Table 1 Flow chart

Visit number	Visit 1	Visit 2	Visit 3	Visit 4	Visit 5	Visit 6	Visit 7	Visit 8	Visit 9	Visit 10	Visit 11	Visit 12	Follow-up
Time related to time of implantation (weeks)	-0.5	0 ¹⁾	0	1.5	3	4	5	7	11	15	16	17	
Visit window (days)				±2 ²⁾	±5	±5	±5	±5	±5	±5	±5	±7 ⁴⁾	²⁾
Name of visit	Screening	Inclusion	Implantation	Device mounting	Start-up visit	One-week observation	Two weeks observation	Four weeks observation	Eight weeks observation	Device explantation	End of study		
Screening, Informed consent	X												
Safety blood measurements	X												
Concomitant illness/medical history	X												
Demography	X												
Physical examination	X				X						X		
ECG	X												
Concomitant medication	X	X	X	X	X	X	X	X	X	X	X	X	
In/exclusion criteria	X	X											
Withdrawal criteria			X	X	X	X	X	X	X	X	X		
Device implantation			X										
Suture removal				X								X	
Photography of device fitting					X								
EEG quality test					X						X		
CGM mounting					X				X				
Mounting of external device				X									
Collecting data for calibration start				X									
Hypoglycaemia alarm "on"					X	X	X	X	X	X	X		
Adverse events registration			X	X	X	X	X	X	X	X	X	X	
Adverse device effect registration				X	X	X	X	X	X	X	X	X	
Induced hypoglycaemia							X				X		
Log book				X	X	X	X	X	X	X	X		
Questionnaire					X			X		X		X	
Device explantation												X	
Surgeon questionnaire			X									X	
UNEEG™ medical staff present			X ⁷⁾	X ⁷⁾	X ⁷⁾	X ⁷⁾	X ⁷⁾	X ⁷⁾	X ⁷⁾	X ⁷⁾	X ⁷⁾	X ⁷⁾	X

¹⁾ Inclusion should take place as soon as all screening (including laboratory results) are available, reviewed and subject is confirmed eligible and no later than two weeks after screening. This visit can be performed as a telephone consultation after reviewing blood samples

²⁾ Removal of sutures should be within a time window of 8-12 days following implantation and explantation, respectively

⁴⁾ The explantation of the implanted device should take place as soon as possible following the end of study visit

⁷⁾ Optional

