The hypoglycaemic alarms will be classified according to categorisation displayed in Table 2 (true and false, positive and negative hypoglycaemia alarms), and presented as described for primary performance endpoint.

Table 2 Categorisation of hypoglycaemic episodes

Episodes categorised as			
PG > 3.9mmol/l	+ alarm	+/- clinical hypoglycaemia ^{a)}	False positive 
	- alarm	+/- clinical hypoglycaemia ^{a)}	True negative 
PG 2.0 – 3.9mmol/l	+ alarm	+/- clinical hypoglycaemia ^{a)}	True positive 
	- alarm	+ clinical hypoglycaemia ^{a)}	False negative 
		- clinical hypoglycaemia ^{a)}	True negative 
PG < 2.0mmol/l	+ alarm	+/- clinical hypoglycaemia ^{a)}	True positive 
	- alarm	+/- clinical hypoglycaemia ^{a)}	False negative 
PG not measured	+ alarm	+ clinical hypoglycaemia ^{a)}	True positive 
		- clinical hypoglycaemia ^{a)}	Not categorised 
	- alarm	+ clinical hypoglycaemia ^{a)}	Not categorised  False negative ^{b)} 

^{a)} According to subject (No strict definition is given)

^{b)} If hypoglycaemic episode was severe (i.e. requiring assistance from third person whether being help for carbohydrate ingestion, glucagon injection or contact to health care person), the episodes should be characterised as false negative

PG; plasma glucose

Data from **EEG quality test** at the visit 4 and visit 10 will be compared graphically.

The **impedance** is expected to be below 5 kOhm at all times. No trend in the measurements for each subject should be apparent over time, except perhaps a small decline in the beginning. Any change in impedance over time (from visit 5 to visit 10) will be summarised descriptively and presented by subject.

The **number of device complaints** will be tabulated and presented by device part.

Mean blood, plasma or interstitial **glucose level at the time of an alarm** will be summarised for insulin-induced hypoglycaemia and spontaneous hypoglycaemic episodes, separately.

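### The device-complaint window (visits 4 to 10) leaves out implantation and explantation, and Table 1 contradicts the ADE endpoint at visit 3

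*Combined protocol and SAP*

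**What the plan says.** **Complaints.** Section 2.2 lists, among the secondary performance endpoints, "Number of device complaints (from visit 4 to visit 10"). Section 7.5.1 says that the number "will be tabulated and presented by device part".

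**Device parts.** Section 5 describes three: the implant with its electrode, the external device (in two versions), and the needle: "An insertion needle for the implantation procedure (Figure 1e"). Section 3.1 places implantation at visit 3. It has the external parts mounted at visit 4 and fitted as needed up to visit 10. Section 4.4 links explantation and suture removal to visits 11 and 12, and a footnote to Table 1 puts explantation after the end-of-study visit.

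**ADEs.** Section 2.2 defines the secondary safety endpoint as "Number of adverse device effects (ADEs) 17 weeks after implantation (from visit 3 to visit 12"), the same span as the primary safety endpoint, "Number of AEs 17 weeks after implantation (from visit 3 to visit 12"). The ADE definition in section 6.1.2.1 names deployment and implantation. Section 6.1.2.2 requires every AE and ADE to be collected, with subjects asked at each contact. In Table 1 the row "Adverse events registration" begins at visit 3, whereas the row "Adverse device effect registration" begins at visit 4.

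**The concern.** A table by device part invites the reader to compare the parts. If one part is used only before counting starts, an empty or absent row for it says nothing about how it performed, yet it can be read as no problems reported. The same holds for the implant at the two moments when it is handled surgically.

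This matters because section 7.1 justifies the sample size by the information it will yield for optimising the algorithm and adjusting procedures, and section 8.10 says the report will serve further development and approval. A needle that is awkward to use, without any untoward response in the subject, need not be recorded as an ADE. It could then appear in none of the planned tables.

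For ADEs the worry is practical. If visit forms are built from the flow chart, the form for the day of surgery may carry no ADE prompt, although the endpoint starts that day.

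**Working it through.** **Inputs.** Table 1, row "Time related to time of implantation (weeks"): visit 3 = 0, visit 4 = 1.5, visit 5 = 3, visit 10 = 15, visit 11 = 16, visit 12 = 17. The windows come from section 2.2. Planned enrolment is 12 to 20 subjects (section 4.1).

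**Reproducing the plan's own figures.**
- AE and ADE window, visit 12 minus visit 3: 17 − 0 = 17 weeks, as stated.
- Monitoring period, visit 10 minus visit 5: 15 − 3 = 12 weeks, as stated.

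The week row can therefore be relied on for what follows.

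**Windows compared.**

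| Count | Visits | Weeks | Length | Implantation inside? | Explantation inside? |
|---|---|---|---|---|---|
| AE endpoint | 3–12 | 0–17 | 17 | yes | yes |
| ADE endpoint | 3–12 | 0–17 | 17 | yes | yes |
| ADE row in Table 1 | 4–12 | 1.5–17 | 17 − 1.5 = 15.5 | not marked | yes |
| Device complaints | 4–10 | 1.5–15 | 15 − 1.5 = 13.5 | no | no |

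**Size of the complaint gap.** 13.5 / 17 = 79% of the period is covered. The omitted time is 1.5 weeks at the start (weeks 0 to 1.5) plus 17 − 15 = 2 weeks at the end, 3.5 weeks in all. Each operation falls in one of these two gaps. Of the three device parts, the needle has none of its stated use inside the window, for any of the 12 to 20 implantations.

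**Size of the ADE mismatch.** The AE row carries 10 marks (visits 3 to 12) and the ADE row 9 (visits 4 to 12). The difference is one visit, or 1.5 weeks, and that visit is the implantation.

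**Does other text close either gap?** For ADEs, yes: the endpoint, the definition and the collection rule in section 6.1.2.2 all reach visit 3. For complaints, no: section 6.1.2.2 speaks of AEs and ADEs only, and section 7.5.1 adds the breakdown by part without altering the window.

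**The case against.** The strongest defence is that the complaint window is deliberate. Complaints are a performance endpoint, and the performance objective in section 2.1.1 concerns daily life and induced hypoglycaemia, not surgery. Visits 4 to 10 are the period of external-device wear, and hours of use are counted over the same visits. Implantation safety is measured by AEs and ADEs, both from visit 3. Section 7.5.1 does not list the rows of the table, so it promises no needle row. Table 1 also shows a surgeon questionnaire at visit 3 and again at the end of the study.

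Much of this stands. The window suits the external device, and the alignment with hours of use is worth keeping. But the plan does not state that the limit is intended, and a breakdown by part is uninformative for a part whose use lies wholly outside the window. No endpoint or planned analysis uses the surgeon questionnaire, and its content is not given.

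A second objection is that the table may have lost its column alignment when read from the PDF. The EEG quality test appears there under visits 5 and 11, while section 7.5.1 gives visits 4 and 10, and some visit names look displaced. This doubt is fair. Against it, the ADE row has one mark fewer than the AE row and both end at visit 12, so a start at visit 4 is the likelier reading, though not a certain one.

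A reader might infer that implantation falls outside all device counts, or that the primary safety objective is left unmeasured. The documents do not support either. The ADE count is defined from visit 3, its definition names the implantation, and every ADE must be collected.

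**Conclusion.** Two separate findings hold, both minor.

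1. The complaint count omits implantation and explantation: 3.5 of 17 weeks, both operations, and all stated use of one of the three device parts. This assumes that a complaint is placed in time by the event it concerns. The plan does not define a complaint, and a needle problem first reported at visit 4 might be counted on another reading.

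2. Table 1 and the ADE endpoint disagree at visit 3. This is an internal contradiction with a risk that ADEs are not prompted for on the day of surgery. It is not an exclusion from the ADE count, and it depends on the table's columns having been read correctly.

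No primary endpoint or analysis set is affected, and no comparative analysis is planned. What is at stake is whether one secondary table tells the reader what its layout implies.

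**What to change.** - In section 2.2, count device complaints from visit 3 to visit 12. In section 7.5.1, tabulate them by device part over that span, with visits 4 to 10 as a separate line so that the figure still lines up with hours of use.
- In Table 1, mark ADE registration at visit 3 so that it agrees with the endpoint. If the source table already carries that mark, nothing is needed.
- If the sponsor prefers to keep visits 4 to 10 alone, state the reason and show the needle as not assessed instead of zero.

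The cost is a few wording edits and one extra line in a table, with no new visit or procedure. The complaint count may rise slightly.

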3.1 Description of study design

The present study is a 4-month non-controlled observational study in subjects with type 1 diabetes. Subjects will attend a screening visit (visit 1) in order to assess their eligibility, followed by an inclusion visit (visit 2) which should take place as soon as all screening results (including laboratory results) are available, reviewed and the subject is confirmed eligible. 12-20 subjects are planned to be enrolled, and withdrawals will be replaced until at least 12 subjects have completed the study.

The subjects will have the implantable part of the hyposafe H02 device implanted (see Figure 1). Subjects will be exposed to insulin-induced hypoglycaemia twice during the study. A device for continuous glucose monitoring (CGM) will be mounted for two periods of approximately 5 days. They will wear the hyposafe H02 device as much as possible both during daytime and night-time. In addition, they will fill out questionnaires and complete an interview regarding use, discomfort and satisfaction related to the implantation and the use of the H02 device.

Subjects will have the implantable part of the hyposafe H02 device implanted at visit 3 by a surgical procedure under local anaesthesia. External parts of the hyposafe H02 device will be mounted at visit 4 and fitted if needed at each subsequent visit until visit 10 (see flow chart Table 1).

The duration of the study from screening (visit 1) to removal of sutures (visit 12) will be approximately 18 weeks.

This study will be conducted in accordance with this investigational plan, ISO 14155:2011, ethics committee requirements, the Declaration of Helsinki (23), applicable local governmental regulations, and appropriate regulations for clinical studies.

4 Study population

4.1 Definition of the overall subject population

Between 12 and 20 subjects with type 1 diabetes and impaired awareness of hypoglycaemia will be enrolled in the study to ensure a number of subjects completing the study of at least 12.

4.2 Inclusion criteria

For a subject to be eligible, all inclusion criteria must be answered “yes”:

1. Informed consent obtained before any study related activities³
2. Type 1 diabetes diagnosed at least five years prior to inclusion in the study
3. Age 18-70 years
4. Impaired awareness, i.e. defined as unaware by the Pedersen-Bjergaard scale (section 6.1.5) *and/or* history of at least one severe hypoglycaemia⁴ within the preceding year

4.3 Exclusion criteria

For a subject to be eligible, all exclusion criteria must be answered “no”:

1. Severe cardiac disease
 - History of myocardial infarction
 - Cardiac arrhythmia
2. History of stroke or cerebral haemorrhage and any other structural cerebral disease
3. Active cancer or cancer diagnosis within the past 5 years
4. Uraemia defined as s-creatinine \geq 3 times upper reference value
5. Liver disease defined as s-ALAT \geq 3 times upper reference interval
6. Epilepsy
7. Use of antiepileptic drugs for any indication
8. Clinically important hearing impairment
9. Use of active implantable medical device including
 - Pacemaker and ICD-unit
 - Cochlear implant
10. Use of following drugs:

³ A study related activity is any procedure that would not have been performed during the normal management of the subject

⁴ Requiring assistance from third person whether being help for carbohydrate ingestion, glucagon injection or contact to health care person

- Chemotherapeutic drugs of any kind
- Methotrexate
- Third generation antipsychotic drugs (aripiprazole, quetiapine, clozapine, ziprasidone, paliperidone, risperidone, sertindole, amisulpride, olanzapine)

11. Contraindications to the local anaesthetic used during implantation (1% xylocain with adrenalin)

12. Known or suspected abuse of alcohol defined as consumption of >250g alcohol⁵ or any other neuro-active substances

13. Infection at the site of device implantation

14. Any haemorrhagic disease

15. Females of childbearing potential who are pregnant or intend to become pregnant or are not using adequate contraceptive methods⁶ throughout the study

16. Performing extreme sport, including scuba diving (snorkel diving is allowed) or parachute jumping

17. Incapable of understanding the subject information or unlikely to complete the study for any reason

18. Operating MRI scanners

19. Operating handheld transceivers for communication (e.g. within the police, medical, fire, air traffic control, marine or military)

20. Working at broadcast stations for television or FM/DAB radio

Subjects who are non-compliant with any of the eligibility criteria, but included in the study, should be excluded immediately. If extraordinary circumstances speak in favour of maintaining the subject in the study then this is only acceptable if justified and approved by the ethics committee and if regulatory authorities are notified.

4.4 Withdrawal criteria

1. The subject may withdraw at will at any time without explanation
2. The subjects may be withdrawn from the study at the discretion of the investigator due to a safety concern or if judged non-compliant with the study procedures

Subjects must be withdrawn from the study for any of the following reasons:

3. Included in the study in violation with any of the inclusion and/or exclusion criteria
4. Use of any drug listed under exclusion criteria
5. Subject becomes pregnant during the study

This will not impact the treatment or follow-up of the subject. If a subject is withdrawn from the study, the investigator must aim to undertake procedures similar to those for visit 11 and 12: The

⁵ in Danish: 21 “genstande” per week

⁶ Safe anticonceptive methods includes contraceptive pills, intrauterine device including hormone intrauterine device and sustained gestagen injection

device must be explanted as quickly as possible, the sutures removed when appropriate and the end-of-study-form in the case report form (CRF) must be filled out.

Although a subject is not obliged to give his/her reason(s) for withdrawal, the investigator must make a reasonable effort to ascertain the reason(s), while fully respecting the subject's rights. Any reasons obtained must be specified in the subject's medical file and the appropriate section of the CRF.

5 Description of the hyposafe H02 device

The hyposafe H02 device consists of three parts: An implantable part which consists of a 20 mm semi-spherical implant house and an electrode (diameter: 1 mm, length 100 mm), see Figure 1b. The implant records the EEG signal and transmits the signal wirelessly to the external device. The position of the implant is depicted in Figure 1a. The external device is supplied in two versions: An ear hanger (Figure 1c) and a disc version (Figure 1d) both wirelessly receiving signals from the implant and charging the implant. An insertion needle for the implantation procedure (Figure 1e).

[figure not shown]

Figure 1 Hyposafe H02 device

a) Position of the implant and the external part of the device, b) The implant (left) consists of an electrode and an implant house. The external part (right) demonstrates the earhanger alone, c) Earhanger version of the external device, d) Disc version of the external device, e) Needle for insertion of the electrode

6 Methods and assessments

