6.1.1 Early discontinuation

In case of early discontinuation, either requested by the subject or at the discretion of the investigator, the end-of-study-form must be completed. The subject must be followed up, as appropriate.

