7.1 Rational for the choice of sample size

This is not a comparative endpoint study. It is assumed that sufficient information about the performance, safety and the use of the hyposafe H02 to support any potential optimisation of the algorithm or adjustment of procedures will be obtained with approximately 12 subjects with type 1 diabetes. The total number will depend on the results of the study and number of withdrawals, and it is planned to enrol 12-20 subjects with type 1 diabetes to ensure a number of subjects completing the study of at least 12.

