7.5.3 Usability endpoints

All usability endpoints will be analysed using the FAS.

Development in discomfort over time

Data from questionnaires regarding discomfort related to the implanted device will be tabulated and presented by week and discomfort category and compared over time (visit 5 to visit 10).

Assessment of alarm fatigue

Data from questionnaire regarding alarm fatigue at visit 12 will be tabulated and presented by category of sensitivity and false alarm(s).

User satisfaction

Subject user satisfaction at visit 8 will be summarised based on the specific questionnaire.

Usage of external device

The mean number of hours the hyposafe H02 day or night device has been connected to the implant from visit 4 to visit 10 will be summarised. Summaries will be presented for daytime and night-time, separately.

Response to hypoglycaemia alarm

The number of preventive actions, i.e. the number of hypoglycaemia alarms where subject was able to take preventive action as instructed (acknowledge the alarm by key press, measure blood glucose, and in case of low blood glucose; ingest a carbohydrate rich meal) compared to the total number of hypoglycaemia alarms from visit 5 to visit 10 will be tabulated.

8 Ethics

The study will be conducted according to the Declaration of Helsinki (23) and approved by the local ethical committee before commencement. The use of the hyposafe H02 must be approved by the Danish Health and Medicines Agency before initiation. Only information relevant for the study will be collected. As UNEEG™ medical is a private data responsible the current private health research project will not been notified to the Danish Data Protection Agency. Data will be handled in accordance with the Act on Processing of Personal Data.

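### Early-withdrawal procedures do not call for discomfort, satisfaction or impedance assessments at exit, so late and change-over-time summaries would lean towards subjects who stayed

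*Combined protocol and SAP*

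**What the plan says.** Two sections of the combined protocol and SAP deal with a subject who leaves early.

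- Section 4.4 (Withdrawal criteria) states that "the investigator must aim to undertake procedures similar to those for visit 11 and 12". After a colon it names three items: "device must be explanted as quickly as possible, the sutures removed when appropriate and the end-of-study-form in the case report form (CRF) must be filled". It adds that "the investigator must make a reasonable effort to ascertain the reason(s), while fully respecting the subject's rights", and that any reason obtained goes into the medical file and the CRF.
- Section 6.1.1 (Early discontinuation) states that "the end-of-study-form must be completed. The subject must be followed up, as appropriate". It does not mention explantation, sutures or any assessment.

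The endpoints concerned are timed in sections 2.2, 7.5.1 and 7.5.3. Discomfort data are to be "tabulated and presented by week and discomfort category and compared over time (visit 5 to visit 10". Satisfaction is assessed at visit 8, and change in impedance runs from visit 5 to visit 10. EEG quality results "at the visit 4 and visit 10 will be compared graphically".

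On numbers, section 3.1 says "withdrawals will be replaced until at least 12 subjects have completed the study", and section 7.1 says "it is planned to enrol 12-20 subjects with type 1 diabetes to ensure a number of subjects completing the study of at least 12". The full analysis set (FAS) in section 7.2 holds every included subject. Section 7.4, the only text on missing data, promises a table of reasons for withdrawals that are not related to the device and says nothing about those that are.

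**The concern.** In a small feasibility study of an implant, a subject who leaves because of discomfort, alarm burden or a failing signal carries some of the most useful information. If that subject's last discomfort score, satisfaction and impedance are not collected on the way out, the visit 10 tables contain only those who reached visit 10, and the satisfaction table only those who reached visit 8. Replacement then brings the number of completers up to the target whatever the attrition was. Discomfort could appear to fall over time although nobody improved. EEG quality and impedance cannot be measured once the implant is out, so a final reading missed at exit is lost. All of these are secondary endpoints, but the study is meant to inform optimisation of the device and its procedures before a larger study (sections 1.2 and 7.1).

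**Working it through.** **Step 1. Which assessments does the exit rule reach?** Visit timings come from sections 2.2, 7.5.1 and 7.5.3 and from Table 1 as extracted.

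| Assessment | Where the plan places it | Reached by visits 11 and 12? | Named in 4.4 or 6.1.1? |
|---|---|---|---|
| Discomfort questionnaire | visit 5 to visit 10 | no | no |
| Satisfaction questionnaire | visit 8 | no | no |
| Impedance | visit 5 to visit 10; no row in Table 1 | no | no |
| EEG quality test | visits 4 and 10 (7.5.1); columns 5 and 11 (Table 1) | unclear | no |
| Log book | columns 4 to 11 (Table 1) | visit 11 | no |
| Alarm-fatigue questionnaire | visit 12 | visit 12 | no |
| AE and ADE registration | through visit 12 | yes | no |

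The first three rows are not reached on any reading. The EEG row depends on which visit number is meant. The last three are reached if the three named items in section 4.4 are examples, and are in doubt if that list is complete.

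**Step 2. How many subjects could be affected?** The plan gives no withdrawal rate, so there is no figure of its own to reproduce. With N enrolled and exactly 12 completing, withdrawals are w = N − 12:

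- N = 12: w = 0
- N = 14: w = 2, 2/14 = 14%
- N = 16: w = 4, 4/16 = 25%
- N = 20: w = 8, 8/20 = 40%

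These are enrolment counts. Inclusion (visit 2) comes before implantation (visit 3), so the number implanted may be smaller.

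**Step 3. Effect on the discomfort table (assumed counts).** Let 16 subjects answer at visit 5, d = 6 of them with discomfort, w = 4 leave before visit 10, and nobody's status change. If k of the leavers had discomfort, the visit 10 proportion is (d − k)/(16 − w):

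- visit 5: 6/16 = 37.5%
- visit 10, k = 4: 2/12 = 16.7%
- visit 10, k = 2: 4/12 = 33.3%
- visit 10, k = 1: 5/12 = 41.7%
- visit 10, k = 0: 6/12 = 50.0%

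If leaving were unrelated to discomfort, the expected k would be 4 × 6/16 = 1.5 and the table would barely move. The apparent improvement arises when the leavers are mainly those with discomfort. Within-subject change among the 12 who stayed is zero in every row.

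**Step 4. Bounds for a yes/no end-of-use result (assumed results).** With s favourable among 12 completers and w results missing, the proportion among all enrolled lies between s/(12 + w) and (s + w)/(12 + w):

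- s = 12, w = 4: 12/16 = 75% to 16/16 = 100%
- s = 12, w = 8: 12/20 = 60% to 20/20 = 100%
- s = 10, w = 8: 10/20 = 50% to 18/20 = 90%, against 10/12 = 83% among completers

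**The case against.** A reader might infer that withdrawn subjects give no end-of-use data at all, or that the usability and EEG results describe only those who stayed. The documents do not support either.

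- Section 4.4 points to the procedures of visits 11 and 12 and not only to its three named items. Those visits carry AE and ADE registration, the alarm-fatigue questionnaire and, in Table 1 as extracted, the log book and an EEG quality test.
- Reasons for leaving must be sought and recorded, so discomfort, alarms or poor signal can be captured, although the subject need not answer.
- Usability is analysed in the FAS, and performance in the FAS and the per-protocol set. Replacement removes nobody from the FAS. Log-book entries, alarm responses, hours of use, complaints and completed questionnaires remain up to exit. Impedance change is shown by subject, so a leaver's earlier readings would still appear.

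A reader might also infer that sections 4.4 and 6.1.1 contradict each other. They do not: section 6.1.1 is less complete, and a site that follows both does what section 4.4 says. Nor should 12 satisfactory tests be read as a true rate of 12/20; that lower bound scores every missing result as a failure.

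All of this stands, and it narrows the point. It does not remove it, because membership of the FAS creates no exit value. The position of one mark in an extracted table also cannot settle whether the EEG test applies at withdrawal; a column shift in extraction may explain the mismatch with section 7.5.1.

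**Conclusion.** The point holds in a limited form. Discomfort, satisfaction and a final impedance reading are not called for at early exit, and coverage of the EEG quality test is unclear. If subjects withdraw, the late time points and change-over-time summaries for these endpoints will be weighted towards those who stayed. Section 7.4 adds to this by leaving out the reasons for device-related withdrawals, which are the most informative ones.

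The size cannot be known from the documents. With no withdrawals there is no effect. At the planned maximum of 20 enrolled and 12 completing, up to 8 of 20 (40%) could lack end-of-use values. The fall from 37.5% to 16.7% rests on assumed counts and on all four leavers coming from the six with discomfort. The primary performance and safety endpoints are not the subject of this point. It is a cheap improvement and not a flaw that undermines the study.

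**What to change.** 1. Reconcile sections 4.4 and 6.1.1 so that sites have one list for early exit. This need not change the explantation rule or its timing.
2. Add to that list that, where the subject agrees, the discomfort questionnaire, the satisfaction questionnaire (if not yet done), the EEG quality test and an impedance reading are completed at the last contact before explantation. Confirm that the log book and the alarm-fatigue questionnaire are included, and align the EEG test visit between section 7.5.1 and Table 1.
3. In sections 7.5.1 and 7.5.3, show discomfort by visit and final EEG quality with the number implanted as denominator (the safety analysis set of section 7.2). Add a separate row for subjects withdrawn, with reason, not scored as failures. Describe change in discomfort within subject.
4. Extend the tabulation of reasons in section 7.4 to device-related withdrawals.

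The cost is protocol wording and a few table rows. The forms and tests already exist, and the subject comes in for explantation anyway. The downside is a slightly longer last contact, and some subjects will decline.
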